- Portable central processing unit to integrate all environmental information and relay the information in informative ways back to the user using the various forms of sensory feedback, including the Argus II system or a head mounted display (HMD), the headphones, and a vibrotactile stimulator.

This study is driven by the hypothesis that orientation and navigation performance for users of retinal prosthetics can be greatly improved by incorporating SLAM, stereo/depth based and object recognition technologies conveying spatial environmental information via a combination of artificial vision and auditory and/or haptic feedback. SLAM enables the visual prosthesis system to construct a map of the user's environment and locate the user within that map. Ultimately, we expect that this technology will allow users to create an effective spatial image of the environment, that is, a continuously updated representation of locations in 3D space that supports volitional action for independent navigation with minimal cognitive load.

A2 Purpose of the Study Protocol

This is a prospective observational case series study. We will develop and test a navigational aid system which 1) constructs a map of unfamiliar environments and localizes the user in that environment using SLAM technology 2) automatically identifies navigationally-relevant objects and landmarks in that environment using object recognition and 3) provides sensory feedback via multiple modalities for navigation, obstacle avoidance, and object/landmark identification.

We will test the system's potential with both Argus II users and with normally sighted participants (by simulating a retinal prosthesis via a head-mounted display that emulates the capabilities of the Argus II device).

The human subject tests fall into three groups: in Group 1, target identification and localization tasks test the basic capabilities of the system for conveying characteristics (e.g. shapes, sizes, movement direction) and location information

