The identification and localization tests (Group 1) use common psychophysical judgments such as the following: discriminating between two alternatives by saying which is present in the field of view, touching a tablet computer to indicate the apparent location of a target in the frontal plane, and looking for targets by rotating the head and pointing when one is found. In the egocentric localization and spatial updating tasks (Group 2), the participants will make similar psychophysical judgments, but now in the context of movement, for example requiring the participants to walk several meters towards a visible target. For example, in some trials participants may be asked to move backwards to the origin (with aid of a guide), then verbally estimate the distance to the target or point with a joystick toward it. Similarly, in other trials, after walking toward the target with vision present, they may be asked to move forward a short distance without vision and make the same types of judgments.

The second phase of testing (Group 3 tasks), will involve using the information gleaned from the first phase to assess participants' ability to navigate through an unfamiliar environment. This phase will again compare user performance using the

Basic system with user performance using the **Augmented** and **Augmented + Modal** systems where contextual information associated with the task is conveyed to users via enhanced visual, auditory, and haptic modalities.

Our algorithms for mapping the environment and localizing the user will provide the core autonomous navigational capability of the system. As the user traverses their environment, object recognition will be used in concert with the spatial localization and mapping technology to automatically detect key navigational features (e.g., doors, signs, etc.) and store these locations in the map. Once stored in the map, these semantic attributes may then be verbally queried by the user for navigation, e.g., “lead me to the nearest restroom”.

The enhanced imagery generated by the **Augmented** and **Augmented + Modal** systems will be achieved without modifying the Argus II device. The imagery content for these modes will be computed by algorithms of the navigation system and then transmitted via video link to the Argus II for display to the Argus II user.

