These hypotheses will be tested statistically with sighted subjects (see Section F) by measuring proportion correct assessments as well as through bias and precision measurements. Argus II subjects will be assessed individually to determine whether augmentation leads to lower error, and their error will be quantified through comparisons with the sighted subjects.

F Statistical Plan

F1 Sample Size Determination and Power

No significance testing will be possible with Argus II participants due to the small number of people expected to be recruited for each Argus II participant group in this study (approximately 5).

Importantly, however, we will use the sighted subjects, who simulate the performance of Argus II users through the head mounted display conveying information similar to what is perceived by Argus II users, as a baseline. As described in G3, we characterize performance by Argus II users on any given task relative to this baseline.

In particular, for tests with sighted subjects, we use within-subject factorial designs and test with conventional ANOVA statistics; inter-subject correlations between abilities tests can also be computed. We use sample sizes based on prospective power analysis. A sample size of 20-30 subjects was calculated with [9] to achieve

a power greater than 0.80 at the 0.05 level of significance, using effect sizes from previous studies reporting perceived spatial layout in within-subject designs [10]. As a more general point, the experiments use a within-subject design, in which every subject provides a replicate of the entire study. In psychophysical research (i.e., where a physical variable is parametrically explored), these designs are typically done with populations on the order of 10-20 participants. The proposed sample is also consistent with similar studies of navigation by spatial updating (e.g., [11]).

F2 Analysis Plan

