For each measure, the Argus II participants will be characterized by the z-score distance of their performance from the sighted participants (as computed with their mean and variance). We will use two other approaches to assess the Argus II participants' performance: (i) Use standards from the literature for basic psychophysical effects, including setting .2 as an effective d' score for 2- choice discrimination, based on Cohen's d effect-size statistics; setting 25% as the expectation for a size difference threshold, and setting a standard of 15° for absolute pointing error based on screening cutoffs in previous work. (ii) Set standards by considering the device capabilities; in particular, use distance expressed in device pixels between target and pointing locations in order to measure localization error. Finally, we intend to test the effects of learning by assessing performance over time. For this, we will fit trends to the measures over repeated trials and assess the linear component for a positive slope.

F3 Statistical Methods

See previous sections for additional information about the methods employed for this study.

G Data Handling and Record Keeping

G1 Confidentiality and Security

Every effort will be made to keep Personally Identifiable Information (PII) associated with the study confidential: (1) subjects will be assigned a code number and only the code number will be used to identify the limited clinical information that will be analyzed; (2) the computers on which the data will be stored are password protected and all of them are located in offices with key locks; (3) written documents concerning the study will be kept in locked cabinets; (4) all personnel involved in human subject testing will have completed the appropriate HIPAA training and be fully aware of the need for confidentiality regarding PII. No health information will be acquired for this study.

G2 Training

All study team members are required to take IRB compliance training. At a minimum, this consists in Basic Human Subjects Research (CITI) training, Health Privacy Issues for Researchers training, and Conflict of Interest and Commitment training per JHM IRB policy, in addition to Good Clinical Practice training as required by NIH. PIs are also required to take Research Ethics Workshops About Responsibilities and Duties of Scientists training.

G3 Records Retention

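### F2's d' = 0.2 reference for individual Argus II users sits close to chance and carries no per-user interval or comparison with guessing, so the plan does not secure separation from guessing

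*Combined protocol and SAP*

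**What the plan says.** Section F2 first gives each Argus II user a relative position: "the Argus II participants will be characterized by the z-score distance of their performance from the sighted participants". It then adds fixed standards. The one for 2-choice tasks is "setting .2 as an effective d' score for 2- choice discrimination, based on Cohen's d effect-size statistics". The others listed (a 25% size threshold, a 15° pointing error, localization error in device pixels) concern different tasks.

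Section D1 describes the 2-choice judgment, as one example among several, as "discriminating between two alternatives by saying which is present in the field of view". This is closest to a single-presentation task, although the format is not fully fixed.

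Section E6 states that "Argus II subjects will be assessed individually to determine whether augmentation leads to lower error". Section F1 states that "No significance testing will be possible with Argus II participants due to the small number of people expected to be recruited".

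No section gives the trials per user, task and system. The nearest is F2's learning analysis: "we will fit trends to the measures over repeated trials and assess the linear component for a positive slope". No section gives an interval or standard error for d', or a comparison of 2-choice performance with guessing. F3 only refers back to the earlier sections. Section A2 sets the context: "This is a prospective observational case series study".

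**The concern.** A reference value this close to chance says little about one person unless the precision of that person's score is known. The z-score does not fill the gap. It places a user relative to sighted people on a simulator, who may themselves be near chance if the simulated task is hard. For 2-choice discrimination, d' = 0.2 is therefore the only absolute yardstick in the plan.

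F1's reason for doing no testing is the number of people. That rules out inference to a population of Argus II users. It does not rule out an interval for one user's d', where the replicates are that user's trials. An analyst following the plan would have a bare point estimate to set beside 0.2, and a user who cannot tell the alternatives apart could be written up as showing effective discrimination.

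**Working it through.** **Inputs.** From the plan: d' = 0.2 (F2), two alternatives (D1), assessment user by user (E6). Not in the plan, so assumed and shown as a range: 20 to 400 trials per user and condition, independent trials, an unbiased observer, and a rule that compares the point estimate with 0.2. The plan derives nothing from 0.2, so there is no figure of its own to reproduce.

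**Step 1: d' as percent correct.** Single presentation: Φ(d'/2) = Φ(0.1) = 0.540. 2AFC: Φ(d'/√2) = Φ(0.1414) = 0.556. Chance is 0.500.

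**Step 2: how often a pure guesser reaches 0.2.** For 2AFC this is the exact binomial tail P(X ≥ k) with p = 0.5, where k is the smallest count at or above 55.6%: k = 12 of 20, 28 of 50, 56 of 100, 112 of 200, 223 of 400. For single presentation, hits and false alarms (half the trials each) are enumerated exactly, with d' = z(H) − z(F) and the log-linear correction.

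**Step 3: the same, if a two-sided 95% interval must also lie above 0.** In 2AFC the Clopper-Pearson interval for percent correct is mapped to d' = √2·z(p). In single presentation the interval is d' ± 1.96·SE, with SE from hits and false alarms.

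| Trials | Guesser, point estimate ≥ 0.2: single / 2AFC | Guesser, interval also above 0: single / 2AFC | True d' = 0.2, both met: single / 2AFC | True d' = 1, both met: single / 2AFC |
|---|---|---|---|---|
| 20 | 41% / 25% | 2.1% / 2.1% | 5% / 6% | 38% / 66% |
| 50 | 25% / 24% | 1.7% / 1.6% | 6% / 9% | 74% / 96% |
| 100 | 19% / 14% | 2.7% / 1.8% | 13% / 16% | 98% / 100% |
| 200 | 12% / 5% | 2.5% / 2.0% | 20% / 32% | 100% / 100% |
| 400 | 6% / 1% | 2.6% / 1.2% | 36% / 50% | 100% / 100% |

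Without the log-linear correction (except at rates of 0 or 1), the single-presentation guesser figures are 41%, 34%, 24%, 14% and 6%. The conclusion does not depend on the estimator.

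**Hand check, single presentation, 100 trials.** At d' = 0, SE = √(2 × 0.25/50)/0.399 = 0.251. Then 0.2/0.251 = 0.80, and the upper tail is 0.21, close to the exact 0.19. The half-width is 1.96 × 0.251 = 0.49, more than twice the reference value.

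**Step 4: trials at which a score exactly at the reference separates from 50%** (two-sided 5%): n = (1.96 × 0.5/(p − 0.5))². Single presentation: (0.98/0.0398)², about 606. 2AFC: (0.98/0.0562)², about 304.

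**Step 5: what the point estimate does for a user truly at 0.2.** It reaches 0.2 in about 44-56% of runs at 20 to 400 trials. Comparing the point estimate with 0.2 is therefore close to a coin toss for such a user.

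**The case against.** The strongest reply is that 0.2 is only descriptive. The study is a case series, the hypotheses are tested in sighted subjects, and no test depends on this value. F2 lists it among literature standards and never says that a user at or above it will be declared successful. E6's individual assessment asks whether augmentation lowers error, which is a contrast between systems and not a comparison with chance. All of this stands. It keeps the point minor and makes the pass rule an assumption. What remains is that the plan calls the value effective and gives a reader no means of judging whether a user's score differs from guessing.

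A reader might also infer that a user who meets 0.2 cannot be told from a guesser. The documents do not support that. Separation depends on a trial count that they do not state. In 2AFC a guesser reaches 0.2 in only 5% of runs at 200 trials and 1% at 400, and at 400 adding the interval changes nothing. A user well above 0.2 is separated with far fewer trials. The eligibility criteria allow 4-6 hours a day on 3-5 days, so large counts are possible, but that time is shared across all tasks and three systems.

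Nor is the task format wholly missing, since D1 describes it in part. And a low reference value is not wrong in itself.

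**Conclusion.** The point holds as a minor one. F2 attaches a favourable label to a value 4 to 6 percentage points above chance, for users assessed one at a time, without a per-user interval or a comparison with guessing. F1's reason for omitting inference does not reach an interval over one user's trials.

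The size depends on assumptions: a point-estimate rule, independent trials and no response bias. Under these, mislabelling of a guesser ranges from 41% (20 trials, single presentation) to 1% (400 trials, 2AFC). With the interval condition it is 1.2-2.7% throughout that range. The supportable conclusion is that the plan as written does not secure separation from guessing. It does not follow that separation is impossible or that 0.2 must be replaced. A missing trial count or format alone would be only a gap in detail; the substantive fault is the bare comparison with a near-chance value.

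**What to change.** In F2:

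1. Report each Argus II user's d' for each condition with a two-sided 95% interval over that user's trials, shown beside chance (d' = 0). An interval from hits and false alarms suits single presentation; an exact interval for percent correct, converted to d', suits 2AFC.
2. Do not describe a user as showing effective discrimination when that interval includes 0; report the result as inconclusive.
3. Keep 0.2 as a descriptive reference, with its percent-correct equivalent (54% or 56%).
4. Confirm the task format and the trials per user and condition, so that the interval can be computed.

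This takes a few sentences and no new participants. E6 already plans to evaluate sighted subjects "by measuring proportion correct assessments as well as through bias and precision measurements", and F2 compares Argus II users with them on each measure, so no new measure is needed. F1's statement can stay if it is limited to inference across people. If performance drifts with learning, which F2 intends to examine, the interval describes average performance over the trials pooled and should say so.

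The cost is more inconclusive results at low trial counts. At 100 trials, about 87% (single presentation) or 84% (2AFC) of users truly at 0.2 would not be separated from chance. For a true d' of 0.2, the interval excludes 0 in 80% of runs only at about 1,240 or 620-660 trials. Users with a true d' of 1 are still identified in about 98% or 100% of runs at 100 trials.

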about objects that would be targets for navigation or action. In this group, participants will be stationary and only be asked to rotate/pan their head to acquire camera-generated targets. In Group 2, egocentric localization and spatial image updating tasks test how well the system provides spatial parameters, particularly distance, from optical flow and non-visual sources, leading to the formation of the spatial image. Finally, Group 3 tasks test the system in its function of guiding navigation and assess learning effects.

In all three groups, various instantiations of the system are contrasted as follows. The **Basic system** is the standard Argus II device. The **Augmented system** enhances the imagery for visual feedback compared to the standard Argus II system by decluttering the scene and adding discriminative features to convey object identities. The features to be utilized will be determined after tests in Group 1, but the general goal is to add spatial and/or temporal uniqueness without cluttering the display. The third system, the **Augmented + Modal system**, adds non-visual cues. Initially, we are targeting two non-visual augmentation modalities including (i) verbal and non-verbal auditory feedback along with spatial sound for purposes such as to convey the identity, distance, and direction of objects relative the user and (ii) haptic feedback for purposes such as to direct users how to adjust their head azimuth and elevation in order to acquire a landmark or waypoint within their field of view.

The enhanced imagery information for visual feedback used in the Augmented and Augmented + Modal modes of the system will be computed by the navigation system developed in this study and communicated to the Argus II using a built-in video input on the Argus II that enables visual information provided from an external source to be displayed by the user's implant. No alterations, including software or hardware changes, will be made to a participant's Argus II system during this study.

B Background

B1 Prior Literature and Studies

The Argus II system is a fully portable medical device approved by the FDA for commercial sale in the United States under the Humanitarian Device Exemption (HDE) program. It consists of implanted and external components (see Figure 1).

[figure not shown]

Figure 1 - Argus II Retinal Prosthesis System

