We will recruit approximately 25 to 35 normally sighted adults, and approximately 5 to 15 retinal prosthesis users. We will test sighted participants in order to establish baseline levels for processing the information delivered when the optic nerve is healthy and intact. We do not claim that Argus II users will be comparable in performance; in fact, testing will be directed at the implanted users to characterize a range of performance compared to baseline.

Our Johns Hopkins University Applied Physics Laboratory (JHU/APL), Johns Hopkins Medicine Wilmer Eye Institute (JHM/Wilmer), and Second Sight teams have been collaborating for the past several years to advance the capabilities of the Argus II system and improve performance of Argus II recipients, including developing capabilities for object recognition and stereo vision, and have extensive experience in designing and developing SLAM software and algorithms in the field of robotics. In addition to the investigators at Wilmer Eye Institute and Second Sight who have extensive experience in working with retinal prosthesis users, our team includes [name], who has a long history of research working with visually impaired individuals and studying the impact of human neurophysiology and psychology on the design of instruments and devices that can be used as navigational aids for the blind.

C Study Objectives

C1 Primary Aim

The primary aim of this study is to ascertain whether our system allows Argus II recipients to form a “spatial image” of their environment, that is, a continuously updated representation of locations in three dimensional space that supports volitional action for independent navigation.

C2 Rationale for the Selection of Outcome Measures

The outcome measures derive directly from the goals of this study, namely the ability to identify and localize targets, with and without movements, and navigate through a field comprised of these targets.

D Study Design

D1 Overview or Design Summary

Testing will be conducted at JHU/APL, JHM/Wilmer and at JHU Homewood campus.

This study will be conducted with three different sets of participants.

- One set of eligible participants will consist of Argus II users, with a total of approximately 5 to 15 such participants expected to be recruited for this study. These tests may take place across all test sites.

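### The fixed 15° pointing standard has no no-information benchmark and, in the walk-toward-target-and-return example, cannot detect distance perception or spatial updating

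*Combined protocol and SAP*

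**What the plan says.** F2 (Analysis Plan) judges Argus II users partly by standards taken from the literature. One of them is "setting a standard of 15° for absolute pointing error based on screening cutoffs in previous work". F2 does not say which tasks it applies to, whether it refers to single trials or to a mean, over what range of target directions, or what error an uninformed response would give.

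D1 (Overview or Design Summary) describes the tasks by example. A Group 1 task is "looking for targets by rotating the head and pointing when one is found". The Group 2 example is "requiring the participants to walk several meters towards a visible target". In some trials participants then "move backwards to the origin (with aid of a guide), then verbally estimate the distance to the target or point with a joystick". In others, "after walking toward the target with vision present, they may be asked to move forward a short distance without vision" before making the same judgments. No path aimed away from the target, and no turn, is described.

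A2 says that Group 2 tasks "test how well the system provides spatial parameters, particularly distance". C1 defines the spatial image of the primary aim as "a continuously updated representation of locations in three dimensional space that supports volitional action for independent navigation".

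F1 rules out significance testing in Argus II users. Their other yardsticks are z-scores against sighted participants, the remaining literature standards and error in device pixels (all F2), and each user's own error with and without augmentation (E6).

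**The concern.** A fixed cutoff is informative only if a participant who lacks the ability in question would usually miss it. On a path aimed at the target the bearing does not change, so a habit of pointing straight ahead is correct without any knowledge of how far away the target is or how far one has moved. Distance and updating are what Group 2 and the primary aim are about.

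The z-score does not repair this. Sighted participants on the same layout can also point straight ahead, so a score close to theirs says nothing about updating. Nor is any test planned in Argus II users that would supply a chance level. If passes on such trials were read as support for the spatial image, they would add apparent evidence without content.

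**Working it through.** **1. The plan's figure.** The 15° has no derivation in the documents, so there is nothing to reproduce. The check is what an uninformed response would score against it.

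**2. Inputs.** From the documents: the 15° standard (F2) and the walk, return and forward-move sequence (D1). Assumed, because the documents do not say: joystick pointing is scored in azimuth only; target directions in other tasks are uniform on ±A, with A varied; walking distances enter as fractions of the target distance.

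**3. Walking task.** Let θ be the heading error at the start and f the net fraction of the target distance walked when the response is made. The error of a straight-ahead response is

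atan2(sin θ, cos θ − f).

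After the guided return f = 0 and the error equals θ. With the target on the path (θ = 0) it is 0°, and any heading error up to 15° still passes. Perceived distance and updating do not enter the expression.

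For the variant that continues forward without vision:

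| Start heading error | f = 0 | f = 0.25 | f = 0.50 | f = 0.75 | f = 0.90 |
|---|---|---|---|---|---|
| 0° | 0° | 0° | 0° | 0° | 0° |
| 5° | 5.0° | 6.7° | 10.0° | 19.5° | 42.2° |
| 10° | 10.0° | 13.3° | 19.7° | 36.5° | 64.0° |
| Largest heading error that passes | 15.0° | 11.3° | 7.6° | 3.8° | 1.5° |

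The result is therefore firm for the return variant. In the forward variant it weakens as the participant nears the target, and beyond the target straight ahead is wrong by 180°.

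**4. Other pointing tasks.** For a constant centre response, the share of trials within 15° is min(1, 15/A) and the mean error is A/2. The last column is a simulation with 20 trials (an assumed number).

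| Range ±A (assumed) | Trials within 15° | Mean error | P(mean ≤ 15°) |
|---|---|---|---|
| 15° | 100% | 7.5° | 1.00 |
| 20° | 75% | 10° | 1.00 |
| 30° | 50% | 15° | 0.50 |
| 40° | 37.5% | 20° | 0.026 |
| 45° | 33% | 22.5° | 0.004 |
| 60° | 25% | 30° | about 0 |

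Setting A/2 = 15° gives A = 30°. Inside that range a default response meets the standard on average; well outside it, it does not.

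**5. Guessing over the full circle.** 30/360 = 8.3% of trials fall within 15°, with a mean error of 90°.

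**6. When 15° would be informative.** Take a target 5 m away and 30° off the path (illustrative). A participant who keeps the starting bearing is wrong by atan2(5 sin 30°, 5 cos 30° − w) − 30° after w metres: 6.9° at 1 m, 17.0° at 2 m and 32.0° at 3 m. With enough displacement, failure to update would exceed 15°.

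**The case against.** A reader might infer that 15° can be met with no spatial information at all, so that every pass is empty. The documents do not support that. Guessing over the full circle meets it on 8.3% of trials. D1 mentions a guide only for the backward move; if participants steer the outward walk themselves, their heading already carries direction information obtained through the device. What the return trial lacks is information on distance and updating. In the forward variant, a 5° heading error becomes 19.5° after three quarters of the distance, so a straight-ahead response can fail.

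Three further points stand:

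- D1 gives examples, so other layouts may exist.
- For frontal targets the argument depends on an undocumented range and fails for wide layouts.
- F2 lists 15° among several yardsticks and nowhere says that meeting it demonstrates a spatial image. A user who pointed straight ahead in every condition would show no gain in the Basic versus Augmented comparison, which limits the harm.

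None of this answers the walk-and-return case. There the standard cannot separate a user who updates from one who does not, and the comparison between systems has little room to differ if both give errors near 0°. Verbal distance estimates would be informative, but D1 offers them as an alternative to pointing.

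**Conclusion.** The point holds in limited form. The 15° standard has no no-information benchmark, and in the return example a straight-ahead response has about 0° error regardless of distance perception or updating. A pass in that task is therefore not evidence for the primary aim. This rests on the path being aimed at the target, as D1 describes, and on azimuth scoring; it needs no assumption about display size or target range.

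For other pointing tasks the conclusion is conditional: a centre response meets 15° on average only if targets lie within about ±30° (uniform directions assumed). Until the range is stated, the plan cannot show that its standard is stricter than a default response.

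The documents do not support going further and saying that the plan treats 15° as proof, or that the primary aim will be falsely supported.

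**What to change.** In F2, keep 15° as a descriptive reference and state the range of target directions and the summary statistic for each pointing task. Then:

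- For each pointing task, report the error of a constant straight-ahead response on the actual targets beside the observed error.
- Where target bearings vary, add a within-user permutation of responses across targets. It works with few users, but it is uninformative where every bearing is 0°.
- Credit localisation only when the observed error is below these benchmarks.
- Do not count pointing on straight-line walks as evidence of updating. Use the verbal distance estimates on those trials.
- Count pointing as updating evidence only where the path is not aimed at the target or includes a turn. Changing the start position alone does not achieve this, because a participant who still walks at the target keeps it on the line of travel. Such trials should also end away from the origin, where the bearing seen at the start would again be correct.

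The cost is SAP wording and a minor extra analysis of recorded trials, fewer pointing trials that count towards updating, and a modest layout change if off-path trials are added. This is a cheap improvement.
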